10.3 Clinical Laboratory Evaluations

Laboratory parameters (serum chemistry, hematology, coagulation, urinalysis, and serology test) will be presented in data listings. Abnormal values will be flagged as high or low relative to the local lab normal ranges, where applicable. Values that are deemed as abnormal, clinically significant (as collected on the eCRF) will also be flagged in the data listing.

Laboratory variables will be summarized using actual values and changes from baseline to scheduled time points. Laboratory values will also be categorized according to their NCI-CTCAE version 5.0 toxicity grade and tabulated by worst on-study toxicity grade. The baseline value of a variable is defined as the last value obtained on or before the date and time of the first BBT-176 dose.

10.4 Vital Signs

Vital signs (pulse, respiration, blood pressure, oral temperature, and weight) will be summarized by dose cohort for the dose escalation phase and for each expansion cohort using descriptive statistics at baseline and at each post-baseline time point. Actual values and changes from baseline to scheduled time points will also be summarized.

10.5 Physical Examination

Physical examination results will be summarized by shift tables from baseline compared to scheduled post-baseline time-points presenting the number and percentage of patients with normal /abnormal NCS / abnormal CS and not evaluable results.

10.6 Electrocardiogram (ECG)

The ECG data analysis will be conducted based on methodology recommended in the ICH E14 guidance, The Clinical Evaluation of QT/QTc Interval Prolongation and Proarrhythmic Potential for Non-antiarrhythmic Drugs. Descriptive statistics at baseline and at each scheduled post-baseline time point as well as changes from baseline will be summarized for each ECG parameter (heart rate, RR interval, PR interval, QRS interval, QT interval, QT interval corrected using Frederica's formula (QTcF)) by dose escalation cohort, overall patients in Part 1 and each expansion cohort and overall patients in Part 2. The number and percentage of patients with normal, abnormal and abnormal clinically significant categories will be provided for the overall ECG evaluation for each visit by dose escalation cohort.

The RR interval will be calculated from heart rate using the following formula:

- RR (milliseconds) = $60*1000 / [\text{heart rate in beats per minute}]$

Frederica's formula, which corrects the QT interval for the effect of heart rate, is

- QTcF (milliseconds) = $QT / [(RR/1000)^{0.33}]$ or, equivalently, $QT / [(60/\text{heart rate})^{0.33}]$

The RR value derived from heart rate will be used in any derivations (eg, QTcF) rather than the value collected on the eCRF. Further, the derived QTcF values rather than the QTcF collected in the eCRF will be used for all analyses. Both the collected and derived RR and QTcF values will be shown in the listings.

All ECG information as well as change from baseline will be listed by dose escalation cohort and over all patients in Part 1 and each expansion cohort and overall patients in Part 2.

In addition, a categorical summary of abnormal QTcF values will be presented for each dose escalation cohort and overall patients in Part 1 and each expansion cohort and overall patients in Part 2. Additionally, a frequency table with number and percentage of patients with noteworthy QTcF values (> 450 , > 480 and > 500 ms) during the study and of patients noteworthy QTcF changes from baseline (≥ 30 but < 60 ; ≥ 60 ms) will be provided for each dose escalation cohort,

[figure not shown]

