### 11.7 Safety Analysis

Safety variables to be assessed will include AEs, laboratory test results (hematology, clinical chemistry, and urinalysis), ECG, weight, and vital signs.

Adverse event terms recorded on the eCRFs will be mapped to preferred terms using the Medical Dictionary for Drug Regulatory Activities (MedDRA®) version 23.0 or later. The number and percentage of patients with AEs will be summarized for each dose level and overall according to the system organ class and preferred term. Adverse events (including AESI) will be summarized for overall frequency (number and percentage of patients), worst reported severity, and relationship to study treatment for each preferred term per patient. Serious adverse events will be similarly summarized. Listings of deaths, SAEs, and AEs leading to early termination of study treatment or premature withdrawal from study will also be provided.

Laboratory variables will be summarized using actual values and changes from baseline to scheduled time points. Laboratory values will also be categorized according to their CTCAE (v5.0) toxicity grade and tabulated by worst on-study toxicity grade. The baseline value of a variable is defined as the last value obtained on or before the date and time of the first BBT-176 dose.

ECG, weight, and vital signs will also be summarized by actual values and changes from baseline to scheduled time points using descriptive statistics. Changes in QTcF will also be evaluated for the proportion of patients with absolute values > 500 msec and change from baseline > 60 msec.

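### SAP 10.6 derives QTcF with exponent 0.33 rather than the cube root, and counts changes of 60 ms or more where Protocol 11.7 specifies more than 60 ms: two small corrections

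*SAP*

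**What the plan says.** SAP 10.6 (Electrocardiogram) names Fridericia's correction and defines QTcF as QT divided by (RR/1000) to the power 0.33, with a second form that uses 60 divided by heart rate to the same power. On inputs it says that "The RR value derived from heart rate will be used in any derivations". On use it says that "the derived QTcF values rather than the QTcF collected in the eCRF will be used for all analyses". It keeps the recorded values visible: "Both the collected and derived RR and QTcF values will be shown in the listings".

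The frequency table in SAP 10.6 counts patients with QTcF above 450, 480 and 500 ms ("> 480 and > 500 ms) during the study"). It also counts "patients noteworthy QTcF changes from baseline" in two bands: at least 30 but below 60 ms, and 60 ms or more ("≥ 60 ms) will be provided for each dose escalation cohort").

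Protocol 11.7 (Safety Analysis) commits to the proportion of patients with "absolute values > 500 msec and change from baseline > 60 msec". The protocol names Fridericia's formula in exclusion criterion 6 (Section 7.2) and in the abbreviation list, but prints no exponent.

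**The concern.** Two stated specifications are off.

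- **Formula.** The exponent 0.33 is a two-decimal rounding of 1/3. Because the derived value feeds every QTcF summary, the rounding reaches every threshold count and every change from baseline. Its direction is fixed by heart rate: low above 60 bpm, high below.
- **Change cutoff.** A patient whose largest change is exactly 60 ms falls in the SAP's top band but is not an outlier under Protocol 11.7. As far as the SAP text is visible, no table gives the protocol's count of changes above 60 ms.

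These counts are the planned patient-level summary of QTcF outliers. Protocol 4.3.1 cites QTc prolongation for osimertinib and bradycardia for brigatinib as examples of risks that BBT-176 might share, and reports BBT-176 itself as negative on hERG testing. The counts should therefore follow the named formula and the protocol's threshold, although nothing here suggests that a safety signal would be lost.

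**Working it through.** **Inputs.** From SAP 10.6: exponent 0.33, RR = 60,000/heart rate in ms, absolute cutoffs >450, >480 and >500 ms, change bands ≥30 to <60 and ≥60 ms. From Protocol 11.7: >500 ms and change >60 ms. From Protocol 11.1.1: up to 48 dose-escalation patients, used only for scale. Assumed: heart rates of 45 to 120 bpm, and the distributions of change in step 4. The plan states no figure of its own to reproduce.

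**Step 1. Are the two printed forms the same?** RR/1000 = 60/heart rate, so yes, at every rate. Both need the same edit.

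**Step 2. Effect of the exponent on a reading.** The ratio of the SAP value to the cube-root value is (60/HR)^(1/3 − 0.33) = (60/HR)^0.00333.

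| Heart rate (bpm) | Ratio | SAP value when cube-root QTcF is 500 ms | Shift (ms) |
|---|---|---|---|
| 45 | 1.0010 | 500.5 | +0.5 |
| 60 | 1.0000 | 500.0 | 0.0 |
| 75 | 0.9993 | 499.6 | −0.4 |
| 90 | 0.9986 | 499.3 | −0.7 |
| 100 | 0.9983 | 499.1 | −0.9 |
| 120 | 0.9977 | 498.8 | −1.2 |

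At 100 bpm, a reading above 500 ms by the cube root is missed only if it lies between 500 and 500/0.9983 = 500.85 ms. For comparison, with QT fixed at 400 ms, a difference of 1 bpm in heart rate moves QTcF by 2.2 ms at 60 bpm and 1.6 ms at 100 bpm.

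**Step 3. Effect of the exponent on a change.** Take a true rise from 420 to 480 ms.

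- Heart rate 60 at both visits: 480 − 420 = 60.0 ms.
- Heart rate 60, then 100: 480 × 0.9983 − 420 = 479.2 − 420 = 59.2 ms.
- Heart rate 100, then 60: 480 − 420 × 0.9983 = 480 − 419.3 = 60.7 ms.
- Extremes: 58.6 ms for 50 then 120 bpm, and 61.3 ms for 120 then 50 bpm.

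**Step 4. Effect of ≥60 against >60.** The two rules differ only at exactly 60 ms. If changes are held in whole milliseconds and are normally distributed, P(exactly 60) = P(59.5 to 60.5). Taking one change per patient:

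| Assumed mean, SD (ms) | P(≥60) | P(>60) | P(exactly 60) | Expected of 48 |
|---|---|---|---|---|
| 10, 15 | 0.0005 | 0.0004 | 0.0001 | 0.005 |
| 20, 20 | 0.0241 | 0.0214 | 0.0027 | 0.13 |
| 30, 20 | 0.0701 | 0.0636 | 0.0065 | 0.31 |

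SAP 4.2.3 sets rounding for several derived variables but not for QTcF. If the derived value is left unrounded, exact ties almost vanish.

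**The case against.** The strongest reply is that neither difference matters in practice. The exponent moves a 500 ms reading by less than a 1-bpm error in heart rate would. The ≥60 band contains every patient above 60 ms, so it cannot hide a protocol-defined outlier. Changes from baseline are listed by patient, so the protocol's count can be recovered. All of this stands, and it limits the size of the point. It does not make the printed formula the named one, or make the table report the threshold that the protocol states.

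A second reply is that a >60 ms count may exist elsewhere. The last sentence of SAP 10.6 breaks off in the available text, and the section also promises a categorical summary of abnormal QTcF values without giving its categories. This cannot be excluded, so the point is limited to the visible table. The break does come after the change bands have been listed in full.

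A reader might also infer more than the documents support:

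- *That the QTcF threshold counts as a whole depart from the protocol.* The >500 ms cutoff is the same in both documents. The >450 and >480 ms cutoffs are additions in the SAP, and Protocol 11.7 defines nothing for them to contradict.
- *That the SAP wrongly overrides the recorded QTcF.* The protocol requires the machine-derived QTc only for the screening exclusion and does not make the recorded value the analysis value. One pre-specified formula for all patients is a legitimate choice, and the recorded values are still listed. The documents do not say how the machines compute QTcF, so they do not show that the recorded value is more exact.
- *That safety counts are materially distorted.* Any percentage effect rests on assumed distributions of QTcF and heart rate that appear in neither document.

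**Conclusion.** The point holds as a minor correction in two parts. First, the analysis QTcF uses a rounded exponent, with a shift between +0.5 and −1.2 ms at 500 ms over an assumed 45 to 120 bpm and none at 60 bpm. Second, the SAP's top change band (≥60 ms) differs from the protocol's measure (>60 ms), so the visible table does not report that measure. Reclassification is confined to borderline values. At the change cutoff it is well under one expected patient in 48 with whole-millisecond data, and close to none with unrounded data. The heart-rate range and the distributions of change are assumptions. The two mismatches themselves are read directly from the text, given that Fridericia's correction is the cube root. Neither is likely to alter a safety conclusion.

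**What to change.** In SAP 10.6:

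1. Print the exponent as 1/3 in both forms: QTcF = QT/(RR/1000)^(1/3), equivalently QT/(60/heart rate)^(1/3).
2. Change the bands to ≥30 to ≤60 ms and >60 ms, so that the table reports the Protocol 11.7 measure. The lower limit of 30 ms can stay as it is, since Protocol 11.7 sets no boundary there.

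Central derivation and the listing of both recorded and derived values need no change. The cost is two wording edits and the matching program lines, with no new data and no effect on trial conduct.

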## 7.2 Exclusion Criteria

An individual who meets any of the following criteria will be excluded from participation in this study:

1. Treatment with any of the following:
  - An EGFR TKI, including but not limited to osimertinib, afatinib, dacomitinib, gefitinib, or erlotinib within 8 days of the first dose of study treatment.
  - Small molecule targeted inhibitor other than EGFR inhibitor class, or cytotoxic chemotherapy within 14 days; biologic anticancer medicine (cytokines or antibodies, etc.) within 28 days (before the initiation of BBT-176 treatment) for the systemic treatment of advanced NSCLC
  - Major surgery (excluding placement of vascular access) within 4 weeks of the first dose of study treatment
  - Radiotherapy with a limited field of radiation for palliation within 1 week of the first dose of study treatment
  - Patients receiving radiation to more than 30% of the bone marrow or with a wide field of radiation within 6 weeks of the first dose of study treatment
  - Patients receiving CYP2C8 or P-gp strong inhibitor (see Appendix 4)
2. Any unresolved toxicities from prior therapy greater than NCI Common Terminology Criteria for Adverse Events (CTCAE v5.0) Grade 1 at the time of starting study treatment, with the exception of alopecia and Grade 2 neuropathy related to prior platinum-therapy
3. Spinal cord compression or brain metastases, unless asymptomatic and stable fulfilling one of following:
  - Not requiring active treatments prior to start of study treatment
  - Requiring stable dosing regimens of low-dose oral corticosteroid (up to 20 mg prednisone/day or equivalent) for at least 4 weeks prior to the first dose of study treatment
4. Even if the patient has progressed after EGFR TKI therapy, if there is a treatment proven to be effective, the patient should receive the treatment first. This includes cases where documented evidence of *MET* amplification, *HER2* mutation, or SCLC transformation exists and treatments or clinical trials that have been proven for the corresponding mutations are available.
5. Any evidence of severe or uncontrolled systemic diseases, including uncontrolled hypertension and active bleeding diatheses that in the Investigator's opinion makes it

[figure not shown]

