undesirable for the patient to participate in the trial or would jeopardize compliance with the protocol, or active infection including hepatitis B, hepatitis C, and human immunodeficiency virus (HIV). Screening for chronic conditions is not required

6. Any of the following cardiac criteria:
  - Mean resting QTc interval (corrected by Fridericia's formula [QTcF]) > 470 msec obtained from average value of 3 electrocardiograms (ECGs), using the screening clinic ECG machine derived QTc value
  - Any clinically important abnormalities in rhythm, conduction or morphology of resting ECG (e.g., complete left bundle branch block, third degree heart block, second degree heart block, or PR interval of >250 msec)
  - Any factors that increase the risk of QTc prolongation or risk of arrhythmic events, such as heart failure (ejection fraction < 50%; for details refer to [Section 10.2.3.3](#)), hypokalemia, congenital long QT syndrome, family history of long QT syndrome or unexplained sudden death before the age of 40 years in first-degree relatives, or any concomitant medication known to prolong the QT interval
7. Past medical history of ILD, drug-induced ILD, radiation pneumonitis that required steroid treatment, or any evidence of clinically active ILD
8. Refractory nausea and vomiting, chronic gastrointestinal diseases, inability to swallow the study treatment, or previous significant bowel resection that would preclude adequate absorption of BBT-176
9. Involvement in the planning and conduct of the study
10. Judgment by the Investigator that the patient should not participate in the study if the patient is unlikely to comply with study procedures, restrictions, and requirements
11. Previous or concomitant malignancies at other sites, except effectively treated non-melanoma skin cancers, carcinoma in situ of cervix, ductal carcinoma in situ or effectively treated malignancy that has been in remission for more than 3 years and is considered to be cured
12. History or presence of hypersensitivity or idiosyncratic reaction to the study drug(s) or related compounds
13. History or presence of alcoholism or drug abuse within the past 2 years prior to the first dose

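### Worst laboratory grade and the QTcF >450 ms row are counted without conditioning on baseline, so patients who enter abnormal and do not change are included

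*SAP*

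**What the plan says.** **QTcF.** SAP 10.6 plans a frequency table of patients with "noteworthy QTcF values (> 450 , > 480 and > 500 ms) during the study". The same sentence adds rows for "noteworthy QTcF changes from baseline (≥ 30 but < 60 ; ≥ 60 ms". ECG parameters are also summarised at baseline, at each scheduled visit and as change from baseline. The only numerical QTcF limit at entry is Protocol 7.2, exclusion 6, which excludes a screening mean above "470 msec obtained from average value of 3 electrocardiograms". Protocol 11.7 names only >500 ms and a change >60 ms; the >450 ms row is added by the SAP.

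**Laboratory.** SAP 10.3 states: "Laboratory values will also be categorized according to their NCI-CTCAE version 5.0 toxicity grade and tabulated by worst on-study toxicity grade". Protocol 11.7 has the same rule. The baseline-referenced laboratory summary is continuous: "Laboratory variables will be summarized using actual values and changes from baseline to scheduled time points". Protocol 7.1, inclusion 6, admits ALT and AST up to 2.5 x ULN, and bilirubin and creatinine up to 1.5 x ULN. Protocol 7.2, exclusion 2, bars "Any unresolved toxicities from prior therapy greater than NCI Common Terminology Criteria for Adverse Events (CTCAE v5.0) Grade 1", so Grade 1 is admitted.

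**Elsewhere in the SAP.** Section 4.2.1 defines post-baseline as after the first dose, but the two counts above do not use that term. Section 10.5 (physical examination) and section 10.7 (ECOG) plan shift tables from baseline.

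**The concern.** The lowest QTcF cut lies below the entry ceiling, and the laboratory grade table does not show the grade at which a patient started. Both counts therefore mix two kinds of patient: those who became abnormal on BBT-176 and those who were abnormal on arrival and stayed so. The second kind adds a background that has nothing to do with dose. In small cohorts, one such patient can create or hide an apparent difference between dose levels.

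The time window is also loose. Neither on-study nor during the study is defined, so screening and pre-dose values are not expressly excluded. Limiting the window to post-dose values would not be enough, because a patient who enters at 460 ms and stays there is still counted.

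**Working it through.** The documents give no figure to reproduce on this point. The check compares thresholds, then illustrates size under stated assumptions.

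**1. Entry limits against reporting cuts**

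| Reported category | Entry limit | Can an unchanged patient be counted? |
|---|---|---|
| QTcF >450 ms | mean of 3 ECGs ≤470 ms | Yes, if 451-470 ms at entry |
| QTcF >480 ms | same | No; ceiling is 10 ms lower |
| QTcF >500 ms | same | No; ceiling is 30 ms lower |
| QTcF change ≥30 ms | not applicable | No; measured from baseline |
| Worst laboratory grade | residual Grade 1 toxicity admitted; ALT/AST ≤2.5 x ULN, bilirubin ≤1.5 x ULN | Yes, at least where residual Grade 1 is a laboratory toxicity |

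The SAP derives QTcF with exponent 0.33 rather than 1/3. A value of 470 ms becomes 470.29 at a heart rate of 50 and 468.92 at 120, about 1 ms at most, so the comparison stands.

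**2. Do the other rows separate the two kinds of patient?** Take one patient who rises from 430 to 455 ms and one who enters at 455 ms and stays there. Both are counted as >450 ms. Their changes are 25 and 0 ms, both below the first change row at 30 ms, so the frequency table shows them identically. A mean laboratory change likewise cannot show who moved from no grade to Grade 1 and who arrived at Grade 1.

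**3. Share entering above 450 ms.** The documents give no QTcF distribution. Assume a normal distribution with mean m and SD s, truncated at 470 ms:

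P(450 < X ≤ 470 | X ≤ 470) = [Φ((470−m)/s) − Φ((450−m)/s)] / Φ((470−m)/s)

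- m = 410, s = 15: (0.99997 − 0.99617) / 0.99997 = 0.4%
- m = 420, s = 20: (0.99379 − 0.93319) / 0.99379 = 6.1%
- m = 430, s = 25: (0.94520 − 0.78814) / 0.94520 = 16.6%

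**4. One cohort.** Cohort size is redacted; assume 3 to 6 patients. The chance that at least one enters above 450 ms is 1 − (1 − p)^n. For p = 6.1% this is 17% (n = 3) and 31% (n = 6). Over all the assumptions it runs from about 1% (p = 0.4%, n = 3) to 66% (p = 16.6%, n = 6). One such patient adds 1/6 to 1/3, or 17 to 33 percentage points, to that cohort's row.

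**5. Simulation with no drug effect.** Assumptions: patient mean 410-430 ms, between-patient SD 15-20 ms, within-patient SD 8-12 ms, triplicate baseline, eight single post-baseline ECGs. Protocol 10.2.3.2 takes triplicates in Cycle 1, so single readings throughout are a simplification.

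- Counted as >450 ms: 3% to 43% of patients.
- Of patients with baseline >450 ms, 93% to 99% are counted.
- Of patients counted, 8% to 44% had baseline >450 ms.
- At mean 420, SD 20 and within-patient SD 8: 17.7% are counted, of whom 36% had baseline >450 ms. The other 64% crossed the cut through within-patient variation alone.

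**6. Laboratory.** The documents give neither CTCAE cut-offs nor baseline laboratory distributions, so no size is calculated.

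**The case against.** The strongest reply is that the plan is not blind to baseline. The QTcF change rows stand in the same table, ECG and laboratory changes from baseline are summarised, and individual data are listed. This stands, and it confines the point to the two counts named. It does not answer the point, because none of those summaries is cross-classified with the absolute category or grade.

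Second, only one of the five QTcF rows is exposed to the entry ceiling, and the protocol's own QTcF criteria are not. This also stands.

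Third, a reader might infer that baseline QTcF is being reported as drug toxicity, or that these counts distort dose finding. The documents support neither. The SAP calls the QTcF values noteworthy; toxicity is its word for laboratory grades. Under Protocol 12.8, escalation rests on PK, the model-based tool and safety review by the SMC, and the Part 1 primary endpoint is defined through DLTs. The AE tables have their own protection: Protocol 10.6.5 sends conditions present before consent to medical history unless they worsen, and SAP 10.2 defines treatment-emergent AEs by onset on or after the first dose.

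Fourth, the sizes are assumed. The other parts of exclusion 6, such as the bar on QT-prolonging medication, may thin the upper tail. Whether CTCAE v5.0 grades a value differently when it is abnormal at baseline cannot be settled from these documents.

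Fifth, the SAP 10.6 sentence breaks off in the public text, and the layout of a separate categorical QTcF summary is not shown. A baseline cross-tabulation there would meet the QTcF half of the point. The laboratory rule in SAP 10.3 is not cut off in this way.

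**Conclusion.** The point holds for two descriptive counts: worst on-study laboratory grade, and QTcF >450 ms. As written, both include patients who enter abnormal and do not change. The remaining QTcF rows and the continuous changes are sound against the entry limits, but they do not identify those patients.

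Under the assumed distributions, about 0.4% to 17% of patients enter above 450 ms (6% at mean 420 ms, SD 20 ms), and nearly all of them would be counted without any drug effect. The width of that range reflects the absence of a QTcF distribution in the documents. The laboratory effect is real in kind but unsized. No visible test, sample size or decision rule depends on these counts. The case for changing them is that safety is the Part 1 primary objective, the tables are read by dose level, and the correction is cheap.

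**What to change.** In SAP 10.3 and 10.6:

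1. Replace *on-study* and *during the study* with *post-baseline*, as defined in SAP 4.2.1.
2. Add a shift table from baseline CTCAE grade to worst post-baseline grade for each laboratory variable, and one from baseline QTcF category to worst post-baseline category.
3. Report the number of patients whose grade or category is worse than at baseline.
4. State that these counts are read alongside the existing change-from-baseline rows. Within-patient variation still causes threshold crossings, and the worse-than-baseline count does not remove them.

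This follows the form the SAP already uses for physical examination and ECOG. The cost is a wording change and two extra descriptive tables, with no new data.
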